signalled by a set of findings sometimes called Hy's Law that includes an increase in leakage enzymes such as ALT and AST that may signal hepatocyte necrosis along with an increase in bilirubin suggesting a functional deficit. However, in DMD patients this rule is difficult to implement given that patient's AST and ALT are already elevated as part of their disease. Total bilirubin was raised (>ULN) in three of the eight patients during the dosing periods in SMT C11004. GLDH, another leakage enzyme, is thought to be a more reliable indicator of liver cell necrosis particularly in DMD patients and was raised (>ULN) in five of eight patients during the dosing periods. However, the increased GLDH was not dose dependent and the elevation was minimal with only one patient having a value >2x ULN.

In Study SMT C11004, there were no clinically significant increases in QTcF. No patient had a QTcF of >450 ms and no patient had a QTcF value increase by more than 60 ms.

Overall, SMT C1100 was considered safe and well tolerated in study SMT C11004 in paediatric patients with DMD although based on the liver function findings additional monitoring of these parameters and coagulations function (changes in which can also indicate liver damage) will be undertaken in Cohorts 2 and 3.

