4.2.2. Individual Stopping Rules

The pharmacokinetics of SMT C1100 parent and metabolites, and their relationship with all safety parameters, will be reviewed on an ongoing basis by the Sponsor and the DMC. As this is an open-label study, the decision to stop individual patients may be made on a case-by-case basis. The DMC can also recommend, in individual patients, a lowering of the SMT C1100 dose.

If a patient's results meet either of the criteria below, dosing should be stopped and the tests should be repeated as soon as possible. If the repeated results still meet this criterion, the study drug will be permanently stopped and may not be restarted although the patient will continue to be followed for functional and MRI assessments for the duration of the study. If the patient is withdrawn from the study, a follow up visit should be arranged:

- GLDH \geq 3x ULN

Study Number: SMT C11005 Protocol	Compound No.: SMT C1100 Version: 5.0 24Feb2017
---	---

OR

- Bilirubin $\geq 2x$ ULN together with an INR $\geq 1.5x$ ULN (Cohort 2 and 3 only)

Any intolerable AE or SAE that is at least possibly related to study drug should lead to a temporary discontinuation of the patient's study treatment. After resolution of the intolerable AE or SAE, the Investigator, in discussion with the Sponsor, may decide to either permanently discontinue the patient's study treatment, or, if recommended by the DMC and Sponsor reinstate treatment but reduce their *bid* dose to 1.25 g for Cohort 1 and 3 or reduce the frequency to once-daily dosing (2.5 g or 1.25 g for Cohorts 1 and 3; 1 g for Cohort 2; see Section 8.1.1). If a lowered dose is tolerated for at least 2 weeks the Investigator can, based on the recommendation of the DMC and Sponsor escalate the dose up to the original strength. Once-daily dosing should occur in the morning.

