5.0 Definitions and Study Assessments

5.1 Definitions

Baseline

Unless stated otherwise, the baseline is defined as the last non-missing assessment prior to the first administration of investigational medicinal product (IMP). If the assessment time is missing while the assessment date is the same date as the first administration of investigation product, a scheduled pre-dose assessment will be considered as baseline.

Change from Baseline

Change from baseline is defined as (value at post-baseline visit – value at baseline). Similarly percentage change from baseline is defined as $100 \times (\text{change from baseline})/\text{baseline}$.

Concomitant and Prior Medication

Prior medications are defined as medications with a start date prior to first dose of IMP. Concomitant medications are defined as any medications ongoing at the start of IMP treatment or with a start date on or after the first IMP dose date. Consequently, medications ongoing at the start of IMP will be reported as both prior and concomitant medications.

Study Day 1

The first day IMP is administered.

Study Day

Study day is defined as the number of days from Study Day 1.

- Before Study Day 1, Study Day = (Date of Interest – Date of Study Day 1)
- On or After Study Day 1, Study Day = (Date of Interest – Date of Study Day 1) + 1

Therefore the day prior to Study Day 1 is Study Day -1.

Study Visit

For by-visit summaries, data will be assigned to visits using windowing (see below). If more than one actual visit (including the early termination or unscheduled visits) falls within the same defined window, the visit closest to the target day with non-missing data will be considered for analysis. If two actual visit dates are at the same distance from the target day, the latest visit with non-missing data will be considered for analysis.

| Study Analysis Visit | Target Day | Study Day | Interval (days) |
|--|--------------------------|----------------------------|-------------------------------|
| Baseline | 1 | ≤1* | NA |
| Day 7 (Cohorts 2 & 3 only) | 7 | 5 to 9 | 5 |
| Week 4 | 28 | 21 to 38 | 18 |
| Week 8 | 56 | 49 to 66 | 18 |
| Week 12 | 84 | 67 to 112 | 46 |
| Week 24 | 168 | 140 to 196 | 57 |
| Week 36 | 252 | 224 to 280 | 57 |
| Week 48 | 336 | 308 to 364 | 57 |
| Week 60 | 420 | 392 to 448 | 57 |
| Week W | W x 7 | (W x 7 -28) to (W x 7 +28) | 57 |
| And so forth for 3 monthly visits | | | |

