* Must be prior to dosing if time of assessment is recorded.

Windowing will not be used for the biopsy data as there is only one measurement post dose.

These visit windows will be reviewed and may be updated. Any assessments that fall outside of these windows will be reviewed on a case-by-case basis, and decisions on their handling will be fully documented prior to reporting.

Data will be included in analyses regardless of the duration of time since their last dose of study treatment and the assessment. However additional summaries may be generated excluding subjects if their assessment is performed several weeks after their last prior study dose. This will be reviewed on a case-by-case basis as the decision will be dependent on the assessment and the likely impact of the exclusion on the interpretation of the results.

Data collected outside these windows will only be listed.

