5.4.2 Laboratory Data

Laboratory parameters will be reported in International System of Units (SI).

Coagulation parameters will only be assessed in Cohorts 2 and 3.

The table below details the times when laboratory measurements will be taken:

| Visit | Cohort | | |
|------------------|---------------|---------------------|---------------------|
| | 1 | 2 | 3 |
| Screening | H, CC, U, LFT | H, CC, U, LFT, Coag | H, CC, U, LFT, Coag |
| Baseline Phase | H, CC, U, LFT | H, CC, U, LFT, Coag | |
| Day 1 | LFT | LFT | H, CC, U, Coag |
| Day 7 | | LFT, Coag | H, CC, U, LFT, Coag |
| Week 4 | LFT | LFT | LFT |
| Week 8 | LFT | LFT | |
| Week 12 | H, CC, U, LFT | H, CC, U, LF, Coag | H, CC, U, LFT, Coag |
| Week 24 | H, CC, U, LFT | H, CC, U, LF, Coag | H, CC, U, LFT, Coag |
| Week 36 | H, CC, U, LFT | H, CC, U, LFT, Coag | H, CC, U, LFT, Coag |
| Week 48 | H, CC, U, LFT | H, CC, U, LFT, Coag | H, CC, U, LFT, Coag |
| Extension Visits | H, CC, U, LFT | H, CC, U, LFT, Coag | H, CC, U, LFT, Coag |

H: Haematology, CC: Clinical Chemistry, U: Urinalysis, LFT: Liver Function Tests, Coag: Coagulation parameters

Changes from baseline will be calculated.

Some laboratory parameters will be categorized to assist identifying values of potential concern. Details are provided in [Section 9.8.3](#).

The following parameters will be assessed relative to the upper limit of normal, e.g. value/ULN:

- Alkaline Phosphatase
- ALT
- AST
- Creatine kinase
- GLDH
- Total Bilirubin

For those parameters recorded as $>x$ or $<x$ a small value (0.01) will be added or subtracted from the value x respectively prior to performing analyses. Listings will present the original value.

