9.8.3 Laboratory Data

Descriptive summaries of absolute values and changes from baseline will be provided for numerical laboratory parameters for each visit. At each visit the number of subjects with 'High', 'Low' or 'Normal' with respect to their reference range will be tabulated.

The categorical lab results will only be listed.

The number (%) of subjects who fulfill the following liver function test criteria at any time after the start of dosing will be tabulated:

- ALT \geq ULN, $\geq 2 \times$ ULN, $\geq 3 \times$ ULN
- AST \geq ULN, $\geq 2 \times$ ULN, $\geq 3 \times$ ULN
- Total Bilirubin \geq ULN, $\geq 2 \times$ ULN
- alkaline phosphatase $\geq 1.5 \times$ ULN
- GLDH \geq ULN

The number (%) of subjects who fulfill Hy's Law (ALT or AST $> 3 \times$ ULN + bilirubin $> 2 \times$ ULN, Alkaline Phosphatase must also be \leq ULN) will also be tabulated.

Separate summaries will be generated for the first 24 weeks, first 48 weeks and for the whole study.

These parameters will be listed, along with the value related to ULN (i.e. value/ULN) for subjects who fulfill one of the following criteria:

- ALT $\geq 2 \times$ ULN
- AST $\geq 2 \times$ ULN
- Total Bilirubin $\geq 2 \times$ ULN
- alkaline phosphatase $\geq 1.5 \times$ ULN
- GLDH \geq ULN

For each liver function test (ALT, AST, total bilirubin, alkaline phosphatase, GLDH) and creatine kinase, the value related to ULN (i.e. value/ULN) will be plotted against time in trellis plots, where each subject will have their own plot and the legend distinguishing the laboratory parameter. The plot will use a log10 scale with the axis labels reflecting the actual value (e.g. 1, 10, 100...).

For Cohort 2 the number (%) of subjects who fulfill the following coagulation test criteria at any time after the start of dosing will be tabulated:

- International Normalised Ratio $\geq 1.5 \times$ ULN
- Activate Partial Thromboplastin $>$ ULN

Separate summaries will be generated for the first 24 weeks, first 48 weeks and for the whole study.

A listing will also present all data that meet these criteria along with the value related to ULN (i.e. value/ULN).

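### The any-time laboratory tables do not count either of the Protocol's liver stopping criteria as such

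*SAP*

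**What the plan says.** **Stopping rule.** Protocol 4.2.2 sets two liver criteria. One is GLDH of at least 3x ULN, in all cohorts. The other is bilirubin of at least 2x "ULN together with an INR" of at least 1.5x ULN, in Cohorts 2 and 3. When either is met, "dosing should be stopped and the tests should be repeated as soon as possible". The stop becomes permanent only if the repeat still meets the criterion.

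**Any-time tables.** SAP 9.8.3 gives the number and percentage of "subjects who fulfill the following liver function test criteria at any time after the start of dosing will be tabulated". The rows are ALT and AST at 1x, 2x and 3x ULN, total bilirubin at 1x and 2x, alkaline phosphatase at 1.5x, and GLDH at 1x only. Hy's Law is the one joint rule counted. INR of at least 1.5x ULN and aPTT above ULN sit in a separate table that opens "For Cohort 2 the number (%) of subjects who fulfill the following coagulation test criteria". SAP 5.4.2 says "Coagulation parameters will only be assessed in Cohorts 2 and 3".

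**By-visit tables.** SAP 5.1 assigns records to visit windows. If several visits fall in one window, unscheduled ones included, "the visit closest to the target day with non-missing data will be considered for analysis", and ties go to the later visit. It sends out-of-window assessments to case-by-case review with documented handling, and also says "Data collected outside these windows will only be listed".

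**The concern.** Protocol 1.3.4 names liver test change as one of three potential drug-related risks and carries these two criteria into the study to manage it. Safety is a primary objective and laboratory evaluations are a secondary endpoint. A reader of the report will want to know how many boys reached a level that stops dosing, and no planned table says.

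The thresholds are finest where they tell least. ALT and AST get three rows each and feed Hy's Law, although Protocol 1.3.3 says that "in DMD patients this rule is difficult to implement" because both enzymes are already raised by the disease. GLDH, which the Protocol treats as the better liver marker in these boys, gets one row at ULN. Exclusion criterion 4 admits boys with GLDH up to 1.5x ULN, so that row can count a boy whose GLDH never changed on drug.

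**Working it through.** The documents give no planned figure for these events, so the check sets the rules side by side and then tests what the other tables can show.

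**1. Criteria against rows**

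| Protocol 4.2.2 | Any-time count in SAP 9.8.3 | Gap |
|---|---|---|
| GLDH at least 3x ULN, all cohorts | GLDH at least ULN | no 2x or 3x row |
| Bilirubin at least 2x ULN with INR at least 1.5x ULN, Cohorts 2 and 3 | each component alone; INR in Cohort 2 only | no joint row; no INR count in Cohort 3 |

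Hypothetical results show the effect:
- GLDH at 3.4x (stop) and at 1.1x (no stop) fall in the same single row.
- Bilirubin at 2.2x with INR at 1.6x in Cohort 2 adds one to each of two separate rows. Two different boys with one abnormality each would look the same.
- The same pair in Cohort 3 appears in the bilirubin row only.

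**2. Boys covered by the joint rule.** Cohort 2 (about 10) + Cohort 3 (about 15) = 25. Without an any-time INR count: 15/25 = 60%.

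**3. What the GLDH row conveys.** In SMT C11004 (eight boys, F6; Protocol 1.3.3), 5/8 = 62.5% exceeded ULN (exact 95% CI 24 to 91%) and 1/8 = 12.5% exceeded 2x ULN (0.3 to 53%). Applied to the roughly 10 F6 boys in Cohort 2:
- above ULN: 10 × 0.625 = 6.25, about 6 (2 to 9)
- above 2x ULN: 10 × 0.125 = 1.25, about 1 (0 to 5)

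The two thresholds describe very different groups. Neither figure estimates the 3x criterion, because the documents do not say whether the one boy above 2x reached 3x.

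**4. Whether by-visit tables fill the gap.** Let d be the scheduled visit day minus the target day, and r the days from trigger to repeat. With both days inside the window, the repeat is selected when |d + r| ≤ |d|, that is, when d ≤ −r/2. Example at Week 24 (target Day 168, window Days 140 to 196): trigger on Day 160, repeat on Day 165. The distances are 8 and 3, so the repeat is used.

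Permitted visit days on which the repeat replaces the trigger:

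| Visits | r = 1 | r = 3 | r = 7 | r = 14 |
|---|---|---|---|---|
| Weeks 12, 24, 36, 48 (d from −14 to 14) | 14/29 | 13/29 | 11/29 | 8/29 |
| Week 4, Cohort 3 (d from −7 to 7) | 7/15 | 6/15 | 4/15 | 1/15 |
| Weeks 4 and 8, Cohorts 1 and 2 (d from 0 to 7) | 0/8 | 0/8 | 0/8 | 0/8 |

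The delays are assumed, since the Protocol fixes none. These counts show that replacement is possible; they do not measure how often an abnormal value would be hidden. Hiding also needs an improved repeat. Protocol 1.3.5 makes that plausible, reporting a quick return to baseline once F6 was stopped.

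**5. Gaps between windows.** Every Week 4 to Week 48 visit held within its Protocol allowance lies inside its SAP window (Week 24, for example: Days 154 to 182 within 140 to 196). Only unscheduled or late samples can fall in a gap such as Days 113 to 139.

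**The case against.** The case for leaving the tables alone is substantial.

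- **Components are counted.** Bilirubin at 2x is counted in every cohort and INR at 1.5x in Cohort 2, at the Protocol's own thresholds. The joint count cannot exceed the smaller of the two, so a zero in either settles it for Cohort 2. This stands, but it gives no INR bound in Cohort 3 and does nothing for GLDH.
- **Other outputs exist.** Every boy with GLDH at 3x is in the listing triggered at ULN, with his value relative to ULN. GLDH and bilirubin are plotted per subject. SAP 9.2 tabulates discontinuation reasons, SAP 9.8.1 tabulates and lists TEAEs leading to discontinuation, and SAP 9.4.1 counts treatment cessations. This stands, and it keeps the point modest. None of these is a threshold count, however. A boy stopped only temporarily need not appear as a discontinuation, and INR is not in the plots.
- **Confirmation.** A repeat that still meets the criterion remains abnormal in the by-visit data, so replacement can hide only an unconfirmed trigger. This also stands, and it is why triggers and confirmed events should be shown separately.
- **Purpose of the study.** It is small, open-label and descriptive. Stopping decisions follow the Protocol, with Sponsor and DMC review, and the DMC has its own analysis plan, which is not available here. No dosing decision depends on these tables.

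Two stronger readings are tempting. One is that the window rule conceals liver toxicity. The documents do not support this: windowing governs by-visit summaries, the any-time tables are defined without it, out-of-window results are reviewed case by case, and replacement depends on timing and on an improved repeat. The other is that SMT C11004 rates can be scaled to all 55 boys. They cannot: about 45 (30 + 15) receive F3, while the Protocol ties the liver signal to F6.

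**Conclusion.** The point holds as a gap in the safety summary. Neither stopping criterion is counted as such: GLDH is tabulated at a threshold that cannot identify the stopping level, bilirubin and INR are never combined, and about 15 of the 25 boys under the joint rule have no any-time INR count. These conclusions come from reading the two documents against each other and need no assumption beyond the planned cohort sizes. By-visit tables are not a dependable substitute, but how often replacement would occur is unknown.

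No data are lost, and much can be rebuilt by hand. The Cohort 3 part affects only the later Cohort 3 analyses, because under SAP 7.0 the main CSR carries only serious adverse event data from that cohort. Nothing here suggests that a boy who met a criterion would go undetected or stay on drug.

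**What to change.** In SAP 9.8.3:

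1. Add GLDH rows at 2x and 3x ULN to the any-time table.
2. Add an any-time row for bilirubin of at least 2x ULN together with INR of at least 1.5x ULN, in Cohorts 2 and 3. Pair samples within a short stated interval, for example 7 days. A same-date rule could miss an INR drawn soon after a high bilirubin at Week 4 or 8, where liver tests are scheduled without coagulation. Use boys with at least one such pair as the denominator.
3. Extend the any-time INR/aPTT table and its listing to Cohort 3.
4. For both stopping criteria, show first-trigger and repeat-confirmed counts separately.
5. State that any-time tables use all scheduled, unscheduled and out-of-window post-dose results. SAP 5.4.4 already uses unscheduled data for ECG categories.

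A worst-value shift table is optional and can be limited to liver and coagulation parameters. The by-visit selection rule can stay.

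The cost is a few rows and one cohort column to program and check, with no new data. The drawback is that boys with more unscheduled samples have more chances to cross an any-time threshold, so these counts should be read beside the by-visit tables.

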As described above and in the Investigator's Brochure, data from hERG studies with SMT C1100 and its major metabolites (DHD I and DHD III) indicated low risk of hERG channel blockade effects, given the actual plasma levels of DHD I and DHD III seen after dosing with SMT C1100. In study SMT C11003, DHD III levels in the patients with DMD exceeded the maximum level seen in the female rat. However, no significant changes in QTcF were seen in patients with DMD dosed with 2.5 g *bid* for 14 days. Specifically the patient with DMD with the highest SMT C1100 exposure also had the highest level of DHD III following the 1.25 g *bid* dose but did not have the longest QTcF. The maximum mean QTcF of 453 ms was seen in another patient at the 2.5 g *bid* dose level.

In study SMT C11004 examining the F6 formulation, seven of the eight patients experienced at least one TEAE, with all but one event being considered mild or moderate by the Investigator. The one severe event was also the one SAE (raised LFTs). Three patients were withdrawn from the study, two of which discontinued due to TEAEs (raised LFTs (0.25 g *bid* dose) and abdominal pain (1 g *bid* dose)). The most frequently reported TEAEs were diarrhoea (three patients), abdominal pain (two patients), abdominal pain upper (two patients) and pale faeces (two patients). All were considered at least possibly related to treatment, except one patient's diarrhoea and one patient's abdominal pain upper.

Patients with DMD have elevated AST and ALT (of muscle origin) as part of their disease pathology. In non-DMD patients the potential for severe hepatotoxicity may be

Study Number: SMT C11005	Compound No.: SMT C1100
Protocol	Version: 5.0 24Feb2017

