Abnormal liver function tests were seen in patients with DMD dosed with the F6 formulation in the SMT C11004 study. AST and ALT are enzymes already raised in patients with DMD (although the likely source is muscle) and, as such, further elevations in these enzymes due to liver toxicity may be difficult to see. GLDH is being evaluated and is considered a more specific liver enzyme marker [Schomaker *et al*, 2013]. In addition, liver disease is characterised by reduced synthesis of the procoagulant proteins II, VII, IX, X, as well as factor V and factor XI. These factor deficiencies directly affect the standard coagulation measures available in clinical laboratories, mainly the prothrombin time (PT) and its standardisation, the international normalised ratio (INR), and to a lesser extent, the activated partial thromboplastin time (aPTT) [Northup and Caldwell, 2013]. Therefore, as a precaution and as a means to monitor liver dysfunction both GLDH and coagulation times will be measured.

Finally, during the SMT C11004 study stopping criteria based on liver function were developed. These are outlined below and will be followed during this study, as applicable.

If a patient's results meet either of the criteria below, dosing should be stopped and the tests should be repeated as soon as possible. If the repeated results still meet this criterion, the study drug will be permanently stopped and may not be restarted although the patient will continue to be followed for functional and MRI assessments for the duration of the study. If the patient is withdrawn from the study, a follow up visit should be arranged:

GLDH \geq 3x upper limit of normal (ULN)

OR

Bilirubin \geq 2x ULN together with an INR \geq 1.5x ULN (Cohort 2 and 3 only)

Patients in this study will receive either SMT C1100 2.5 g *bid* F3 formulation (Cohort 1 and Cohort 3) or SMT C1100 1 g *bid* F6 formulation (Cohort 2) for 48 weeks. Previous exposure at the F3 formulation 2.5 g *bid* dose level in the paediatric DMD population has

Study Number: SMT C11005	Compound No.: SMT C1100
Protocol	Version: 5.0 24Feb2017

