	serum chemistry parameters) or considered not clinically significant in the opinion of the Investigator. Variations in specific parameters expected in a DMD population (e.g., AST, ALT, alkaline phosphatase, lactate dehydrogenase and CPK) classed by the Investigator as not clinically significant will not exclude the patient			
13	Be willing and able to comply with scheduled visits, drug administration plan, study procedures, laboratory tests and study restrictions	✓	✓	✓
14	Have taken part in a prior SMT C1100 study	NA	NA	✓

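### The ALT/AST threshold counts and the Hy's Law row in SAP 9.8.3 take no account of baseline, in a population whose ALT and AST are raised by muscle disease before the first dose

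*SAP*

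**What the plan says.** SAP 9.8.3 tabulates how many boys meet the "liver function test criteria at any time after the start of dosing will be tabulated". The ALT and AST rows are at or above 1, 2 and 3 x ULN. The other rows are total bilirubin at 1 and 2 x ULN, alkaline phosphatase (ALP) at 1.5 x ULN and GLDH at 1 x ULN. None has a baseline condition.

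The section also counts "subjects who fulfill Hy's Law (ALT or AST" above 3 x ULN, with bilirubin above 2 x ULN, and adds "Alkaline Phosphatase must also be" no higher than ULN.

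The protocol describes the population as follows:

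- Section 1.3.3: "Patients with DMD have elevated AST and ALT (of muscle origin) as part of their disease pathology".
- Section 1.3.3, on Hy's Law: "in DMD patients this rule is difficult to implement given that patient's AST and ALT are already elevated as part of their disease".
- Section 1.3.4: "AST and ALT are enzymes already raised in patients with DMD". It adds that further rises caused by liver toxicity may be hard to see.
- Section 5.2.1.1, criterion 12: "Variations in specific parameters expected in a DMD population (e.g., AST, ALT, alkaline phosphatase, lactate dehydrogenase and CPK" do not exclude a boy if the investigator judges them not clinically significant.

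The study has no control arm (SAP 3.2). Liver function test change is one of three drug-related risks named in Protocol 1.3.4.

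**The concern.** In a single-arm study, the boy's own pre-dose value is the only internal reference. A count of values above a fixed multiple of ULN shows a drug effect only among boys who start below that multiple. If many start above it, the row mostly reports the disease.

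The Hy's Law row carries the same problem into a composite. The protocol itself says the rule is hard to apply in DMD, yet the SAP uses it unadapted. The ALP condition is a second difficulty, because the protocol names ALP among the tests expected to vary in these boys.

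Elsewhere the SAP does use the boy's own baseline. Section 9.8.4 counts boys with 20% changes from baseline in blood pressure and pulse. Section 9.8.5 does the same for PR interval and heart rate, and bands the largest QTcF increase from baseline. The liver tests, where abnormal baselines are expected, get no such count.

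**Working it through.** The plan states no figure for these rows, so there is nothing to reproduce. The check is a reading of the rules plus two illustrations whose inputs are assumptions.

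**1. ALT/AST rows.** Let p0 be the share of boys already above a cut-off before dosing. Let d be the share of boys, at any starting level, whose enzyme the drug pushes up materially. Assume those starting below the cut-off are carried over it. The share tabulated is p0 + (1 − p0) × d. The documents give neither p0 nor d, so p0 is shown as a range with d = 10%. The main study report covers Cohorts 1 and 2, so N = 30 + 10 = 40 (SAP 7.0). With Cohort 3, N = 55.

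| p0 | Row, no drug effect | Row, d = 10% | Shift (points) | Already above, N = 40 | Already above, N = 55 |
|---|---|---|---|---|---|
| 0.5 | 50% | 55% | 5 | 20 | 27.5 |
| 0.8 | 80% | 82% | 2 | 32 | 44 |
| 0.9 | 90% | 91% | 1 | 36 | 49.5 |
| 1.0 | 100% | 100% | 0 | 40 | 55 |

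For example, at p0 = 0.8: 0.8 + 0.2 × 0.1 = 0.82. A count relative to own baseline would show about 10% in every line. At N = 40 that is 4 boys, against 0.2 × 0.1 × 40 = 0.8 of a boy newly entering the ULN row at p0 = 0.8.

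At the level of one boy: stable at 5 x ULN, rising from 5 to 15 x ULN, and falling from 8 to 4 x ULN all score the same in all three rows.

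**2. Hy's Law row, over-counting.** The rule is (ALT or AST > 3 x ULN) and (bilirubin > 2 x ULN) and (ALP ≤ ULN). If muscle enzyme alone meets the first leg, what remains is bilirubin > 2 x ULN with ALP ≤ ULN. Protocol 8.2 says that inhibition of the OATP1B1 transporter by the metabolites may have contributed to one patient's raised conjugated bilirubin. Muscle ALT plus a rise of that kind above 2 x ULN would count as a case without liver-cell injury. The documents do not allow this to be sized. In the earlier F6 study, 3 of 8 boys had bilirubin above ULN (Protocol 1.3.3), but that is 1 x, not 2 x.

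**3. Hy's Law row, under-counting.** Let q be the share of true cases with ALP above ULN. The chance that at least one of k true cases drops out of the row is 1 − (1 − q)^k.

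| q (assumed) | k = 1 | k = 2 | k = 3 |
|---|---|---|---|
| 0.1 | 10% | 19% | 27% |
| 0.3 | 30% | 51% | 66% |
| 0.5 | 50% | 75% | 88% |

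A boy dropped this way is not lost to the report. His biliribin exceeds 2 x ULN, so he is in the bilirubin ≥ 2 x ULN count and listing, and neither depends on ALP.

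**The case against.** The strongest reply is that the sponsor saw the problem and answered it with other outputs:

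- **GLDH.** Protocol 1.3.3 and 1.3.4 present it as the more reliable and liver-specific marker. Boys above 1.5 x ULN at baseline are excluded, and SAP 9.8.3 counts, lists and plots it.
- **Change from baseline.** SAP 9.1 requires quartiles, minimum and maximum as well as the mean, so one large rise would probably appear as the maximum.
- **High/Low/Normal by visit.** Baseline is a defined analysis visit (SAP 5.1), so on a fair reading baseline status against 1 x ULN is already shown.
- **Individual plots.** Each boy's ALT, AST, bilirubin, ALP, GLDH and CK appear over time as value/ULN. With about 55 boys, every plot can be read, and all data are listed.

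Much of this stands. A reader might infer that the liver tables as a whole cannot show injury, or hide it. The documents do not support that, because the bilirubin and GLDH rows and the outputs above remain.

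It does not remove the point. A maximum does not say how many boys rose. High/Low/Normal covers only the 1 x ULN rows. Plots give no count. The GLDH row has a milder form of the same weakness: it counts from 1 x ULN, while entry allows up to 1.5 x ULN.

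A further objection is that a multiple of baseline can also rise from muscle and that no such cut-off has a source in the documents. Both are true, and they limit the fix.

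**Conclusion.** The point holds in a limited form. The ALT and AST count rows cannot by themselves be attributed to drug, because they include boys already above the cut-off before dosing. For the 1 x ULN rows this follows from the protocol's own description. For 2 x and 3 x it depends on p0, which only the baseline data can supply. The Hy's Law row can err in both directions, and neither error can be sized from the documents. No subject-level liver count is relative to baseline, unlike the counts for vital signs and ECG.

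Four stronger readings should be resisted:

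- That the 3 x ULN rows will read close to 100%. The protocol says raised, never by how much.
- That the Hy's Law row simply counts muscle disease. It also needs bilirubin above 2 x ULN, which no section attributes to muscle.
- That ALP will usually be above normal. Criterion 12 says only that variations are expected, without direction, size or frequency.
- That a boy with high bilirubin and high ALP goes uncounted. He leaves one row and stays in the bilirubin count and listing.

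This is a weakness of table design in an unpowered, single-arm study. It is worth correcting because liver change is a named risk.

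**What to change.** Add the following to SAP 9.8.3 and keep the existing rows:

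1. Beside each ULN row, print the number of boys who already met it at baseline, or give a shift table from baseline category to worst on-treatment category.
2. Count boys by worst on-treatment ALT and AST as a multiple of their own baseline, with the same boy's CK ratio alongside. The sponsor's safety physician should confirm the cut-offs. Where the worst value falls at a visit without a CK sample, show CK as missing.
3. Show the Hy's Law row twice, with and without the ALP condition.

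Replacing the Hy's Law row with a rule based on own baseline is not recommended. The documents give no source for such a cut-off, and it could miss a case that the present row would count.

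The cost is SAP wording and a few table rows. ALT, AST, ALP, bilirubin, GLDH and CK are already collected (Protocol 6.4.6.2, SAP 5.4.2). The limit is that a rise over baseline may still come from muscle, so the new rows must be read with CK and GLDH.
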